3.3.3 Exclusion criteria

- 1. Previous systemic anti-cancer therapy within the specified timeframe from the last dose intake to the first dose of trial treatment as shown below:
 - Any non-investigational drug, including anti-angiogenic antibodies (bevacizumab or ramucirumab) and anti-EGFR antibodies (cetuximab or

¹ A woman is considered of childbearing potential (WOCBP), i.e. fertile, following menarche and until becoming postmenopausal unless permanently sterile.

Page 55 of 165

Proprietary confidential information © 2023 Boehringer Ingelheim International GmbH or one or more of its affiliated companies

panitumumab), within 14 days.

- Any investigational drug or other antibodies including immune checkpoint inhibitors, within 28 days.
- 2. Radiation therapy within 4 weeks prior to start of treatment. However, palliative radiotherapy for symptomatic metastasis is allowed if completed within 2 weeks prior to start of treatment but must be discussed with the sponsor.
- 3. Any serious concomitant disease or medical condition affecting compliance with trial requirements or which are considered relevant for the evaluation of the efficacy or safety of the trial drug, such as neurologic, psychiatric, infectious disease or active ulcers (gastro-intestinal tract, skin) or laboratory abnormality that may increase the risk associated with trial participation or trial drug administration, and in the judgment of the Investigator, would make the patient inappropriate for entry into the trial. Any history of stroke or myocardial infarction within 6 months prior to screening.
- 4. Known pathological condition of GI tract, liver and pancreas, excluding the disease under study, that may interfere with assessment of drug safety or may increase the risk of toxicity:
 - a. inflammatory bowel disease
 - b. chronic pancreatitis
 - c. other serious GI pathological conditions by judgment of the investigator e.g. autoimmune disease with GI involvement, unexplained active diarrhea CTCAE grade ≥2 according to CTCAE v5.0.
- 5. Known history of human immunodeficiency virus infection.
- 6. Any of the following laboratory evidence of hepatitis virus infection. Test results obtained in routine diagnostics are acceptable if done within 14 days before the informed consent date:
 - o Positive results of hepatitis B surface (HBs) antigen
 - o Presence of HBc antibody together with HBV-DNA
 - o Presence of hepatitis C RNA
- 7. Active concomitant malignancies, other than the one treated in this trial.
- 8. Chronic alcohol or drug abuse or any condition that, in the investigator's opinion, makes the patient an unreliable trial participant or unlikely to comply with the protocol requirements or not expected to complete the trial as scheduled.
- 9. Women who are pregnant, nursing, or who plan to become pregnant while in the trial; female patients who do not agree to the interruption of breast feeding from the start of study treatment to within 30 days after the last study treatment.
- 10. Presence of uncontrolled or symptomatic brain or subdural metastases. Inclusion of patients with brain metastases who have completed local therapy and are considered stable by the investigator, or with newly identified asymptomatic brain metastases at screening will be allowed. Use of corticosteroids is allowed if the dose was stable for at least 1 week before the baseline MRI.
- 11. Patients who are under judicial protection and patients who are legally institutionalized
- 12. Major surgery (major according to the investigator's assessment) performed within 3 weeks prior to treatment start or planned within 3 months after screening, e.g. hip replacement.
- 13. Any of the following cardiac criteria:
 - a. resting corrected QT interval (QTc) >470 msec

Page 56 of 165

Proprietary confidential information © 2023 Boehringer Ingelheim International GmbH or one or more of its affiliated companies

- b. Any clinically important abnormalities (as assessed by the Investigator) in rhythm, conduction, or morphology of resting ECGs, e.g., complete left bundle branch block, third degree heart block.
- c. Patients with an ejection fraction (EF) <50% or the lower limit of normal of the institutional standard will be excluded. Only in cases where the Investigator (or the treating physician or both) suspects cardiac disease with negative effect on the EF, will the EF be measured during screening using an appropriate method according to local standards to confirm eligibility (e.g., echocardiogram, multigated acquisition scan). A historic measurement of EF no older than 6 months prior to first administration of study drug can be accepted provided that there is clinical evidence that the EF value has not worsened since this measurement in the opinion of the Investigator or of the treating physician or both.
- 14. Known hypersensitivity to the trial medication and/or its components i.e. polysorbate 20, sodium citrate, lysine hydrochloride, sucrose, citric acid.

3.3.4 Withdrawal of patients from treatment or assessments

Patients may discontinue trial treatment or withdraw consent to trial participation as a whole ("withdrawal of consent") with very different implications (refer to Sections 3.3.4.1 and 3.3.4.2).

Every effort should be made to keep the patients in the trial: if possible on treatment, or at least to collect important trial data. Measures to control the withdrawal rate include careful patient selection, appropriate explanation of the trial requirements and procedures prior to trial enrollment, as well as the explanation of the consequences of withdrawal.

The decision to discontinue trial treatment or withdraw consent to trial participation and the reason must be documented in the patient files and CRF. If the reason for treatment discontinuation is death, this should be reported on the SAE form as well, regardless of causal relationship.

3.3.4.1 Discontinuation of trial treatment

An individual patient will discontinue trial treatment if:

- The patient wants to discontinue trial treatment, without the need to justify the decision.
- The patient has repeatedly shown to be non-compliant with important trial procedures and, in the opinion of both, the investigator and Sponsor representative, is not willing or able to adhere to the trial requirements in the future.
- The patient needs to take concomitant medication that interferes with the investigational drug.
- The patient can no longer receive trial treatment for medical reasons (such as cancer progression, surgery, adverse events, other intercurrent diseases, or pregnancy, or nursing).
- The patient experiences an infection with SARS-CoV-2. The patient may resume trial treatment following recovery from SARS-CoV-2 infection if the patient is expected to derive clinical benefit, as agreed between the investigator and sponsor.

Boehringer Ingelheim BI Trial No.: 1412-0001 c17895778-08

Clinical Trial Protocol

Page 57 of 165

Proprietary confidential information © 2023 Boehringer Ingelheim International GmbH or one or more of its affiliated companies

Additional patients may be recruited to replace patients who discontinued their participation early for non-safety related reasons (e.g. unable to attend the protocol defined visits for to personal reason), or trial disruption e.g. measures to control the spreading of COVID-19. Patients may only be replaced after an agreement with the sponsor.

The patient may continue treatment beyond initial RECIST progression if:

- The patient is clinically benefiting,
- The criteria described below are met,
- It is agreed between the Investigator and the Medical Monitor of the Sponsor,
- The patient has signed an informed consent describing this circumstance.

Criteria required to continue treatment through RECIST-defined radiological progression of disease:

- Absence of clinical symptoms or signs indicating clinically significant disease progression
- No decline in performance status
- Absence of rapid disease progression or threat to vital organs or critical anatomical sites [e.g., CNS metastasis, respiratory failure due to tumor compression, spinal cord compression] requiring urgent alternative medical intervention
- No significant, unacceptable or irreversible toxicities related to study treatment

Even if the trial treatment is discontinued, the patient remains in the trial and, given his/her agreement, will undergo the procedures for treatment discontinuation and follow up as outlined in the Flowchart and Section 6.2.3.

3.3.4.2 Withdrawal of consent to trial participation

Patients may withdraw their consent to trial participation at any time without the need to justify the decision.

If a patient wants to withdraw consent, the investigator should be involved in the discussion with the patient and explain the difference between trial treatment discontinuation and withdrawal of consent to trial participation, as well as explain the options for continued follow up after trial treatment discontinuation, see Section 3.3.4.1 above.

3.3.4.3 Discontinuation of the trial by the Sponsor

Boehringer Ingelheim reserves the right to discontinue the trial overall or at a particular trial site at any time for the following reasons:

- 1. Failure to meet expected enrollment goals overall or at a particular trial site.
- 2. Emergence of any efficacy/safety information that could significantly affect the continuation of the trial.
- 3. Violation of GCP, the trial protocol, or the contract impairing the appropriate conduct of the trial.

.

c17895778-08

Clinical Trial Protocol

Page 58 of 165

Proprietary confidential information © 2023 Boehringer Ingelheim International GmbH or one or more of its affiliated companies

The investigator / the trial site will be reimbursed for reasonable expenses incurred in case of trial termination (except in case of the third reason).

3.3.4.4 Replacement of patients for MTD determination and PK evaluation in phase Ia

Patients who experience a DLT during the MTD evaluation period were not replaced. The following patients without DLT during the MTD evaluation period were considered non-evaluable for MTD determination and were not included in the BLRM analysis:

- Patients who withdrew consent or who were lost from follow-up before completing first two cycles of study treatment.
- Patients who have received less than 70% of the planned BI 905711 doses during first two cycles of study treatment
- Patients who missed 2 or more partial or complete visits during the first two cycles of study treatment.
- Patients with missing PK and evaluation of safety parameters.

These patients were replaced for DLT evaluation during the MTD evaluation period if not decided otherwise by the SMC (e.g. if the number of evaluable patients for the current dose cohort is considered sufficient for a dose escalation decision or MTD determination).

Of note, the dose escalation was determined based on all the safety information of all treated patients including those who were not included in the BLRM analysis.

Page 59 of 165

Proprietary confidential information © 2023 Boehringer Ingelheim International GmbH or one or more of its affiliated companies

4. TREATMENTS

4.1 INVESTIGATIONAL TREATMENTS

4.1.1 Identity of the Investigational Medicinal Products

Table 4.1.1: 1 Test product 1

Substance:	BI 905711
Pharmaceutical formulation:	Powder for Solution for Infusion
Source:	Boehringer Ingelheim Pharma GmbH & Co. KG
Unit strength:	100 mg/vial (10 mg/mL)
Posology:	Single administration every two weeks for a patient enrolled in a biweekly regimen. Single administration every week for 3 weeks on, 1 week off for a patient enrolled in a weekly regimen.
Method and route of administration:	intravenous

4.1.2 Selection of doses in the trial and dose modifications

4.1.2.1 Dose(s) selection for Phase Ia

A detailed description of the methods and considerations to determine a safe starting dose and the phase Ia dose levels, taking into account the available nonclinical information, including PK/PD and toxicity data, is described in the current IB (c16856466).

In summary, human pharmacokinetics of BI 905711 upon intravenous administration were predicted based on cynomolgus monkey PK data. Dose-normalized, concentration-time data were scaled to human by means of elementary Dedrick scaling (scaling factors d=1 and b=0.85) with mean body weights of 2.9 and 70 kg for monkeys and humans, respectively.

PK and tumor growth inhibition data from both the COLO205 and GP2d xenograft models were incorporated into dose–response models and used, by means of plasma exposure matching over the proposed 2 week dosing interval (AUC0-336h), to predict the efficacious human dose and relevant dose-range to be investigated in phase Ia. (Figure 4.1.2.1: 1).

Proprietary confidential information © 2023 Boehringer Ingelheim International GmbH or one or more of its affiliated companies

[figure not shown]

Figure 4.1.2.1: 1 Simulated BI 905711 exposure vs. response at 14 days after a single i.v. administration. Cavg (AUC0-336h divided by 336h) vs % Tumor Growth Inhibition relative to untreated control-curves for GP2d (blue) and Colo-205 (black) xenograft PK/PD models. Predicted Cavg (μg/mL) values at the projected human doses levels (mg/kg) are shown as overlay

The recommended starting dose for phase Ia is based on an integrated evaluation of the predicted exposure-response relationship, the HNSTD exposure in the 6-week toxicology study in cynomolgus monkeys, literature review of other TRAILR2 agonists and the proposed patient population (c16856466).

A starting dose of 0.02 mg/kg of BI 905711 with following characteristics has been selected:

- The starting dose is a human equivalent dose (HED) based on matching 14 day predicted plasma exposure with the simulated PK/PD relationship in two xenograft models. This exposure level corresponds to an activity of ~ 30% tumor growth inhibition as compared to maximally active dose in those two models (25% for COLO 205 and 34% for GP2d) as shown in Figure 4.1.2.1: 1.
- The starting dose is 30-fold lower as compared to the modelled maximally active human equivalent dose in the studied xenografts models (0.6 mg/kg).
- The predicted exposure in humans at the starting dose is 1045- and 650-fold below the Cmax and AUC0-336, respectively, at the NOAEL, and >3600-fold below both parameters at the HNSTD in monkeys. Therefore, this starting dose is supported by the 6-week repeat-dose toxicity study in cynomolgus monkeys.

For further starting dose details, refer to the Investigator's Brochure (c16856466).

The dose is planned to be escalated in cohorts at the pre-defined dose levels in Table 4.1.2.1:1. In-between or higher dose levels may be investigated as long as they fulfill the EWOC criterion. Rationale for the provisionally selected dose levels in phase Ia is based on the predicted human pharmacologically active dose and ensures a complete coverage and investigation of the projected BI 905711 dose-response relationship as shown in Figure 4.1.2.1: 1. At any time during the trial, it will not be permitted to escalate to a dose

Page 61 of 165

Proprietary confidential information © 2023 Boehringer Ingelheim International GmbH or one or more of its affiliated companies

which does not fulfill the EWOC criterion (refer to Section 7.1). Dose escalation rules are described in protocol Section 3.1.1 and Section 7.1.

Table 4.1.2.1: 1 Provisional dose levels for dose escalation of BI 905711 in phase Ia

Dose level	Dose (mg/kg)	Increment from previous dose	Minimum number of CRC patients [†]	Number of Non – CRC GI cancer patients##
1	0.02		1 (any)	1
2	0.06	200%	1 (any)	1
3	0.2	230%	4 (include at least 1 Japanese patient)	Up to 4
4	0.6*	200%	4 (include at least 1 Japanese patient)	Up to 4
5	1.2	100%	4 (include at least 1 Japanese patient)	Up to 4
6	2.4	100%	4 (include at least 1 Japanese patient)	Up to 4
7	3.6	50%	4 (include at least 1 Japanese patient)	Up to 4
8	4.8	33%	4 (include at least 1 Japanese patient)	Up to 4

^{*}Predicted optimal biological dose.

At the end of the MTD evaluation period for each treatment cohort, BI convened a meeting with the SMC. At the SMC meeting, the safety data including DLTs during and beyond the MTD evaluation period and PK/PD data as available for each patient in the current dose cohort was presented. Based on that, a decision on the next dose level to be tested was made. Dose escalation continued until identification of the MTD, safety concerns arose, or the trial was terminated for other reasons. Further escalation steps above 4.8 mg/kg could occur if deemed appropriate by the SMC.

4.1.2.2 Dose(s) selection for phase Ib

Dose(s) selection for phase Ib was made by the SMC with the aim to select a safe and potentially effective dose range of BI 905711 and is based on integrated analysis of all data collected in phase Ia (including safety, PK, biomarker, tumor response)

Selected dose(s) cannot be higher than the MTD observed in phase Ia, if the MTD was determined.

A patient will receive BI 905711 either as a single administration every two weeks or as a single administration every week for 3 weeks on, 1 week off depending on which dose

[†]The number of patients in the dose escalation cohorts may be increased in case of DLT observation.

[#] If the first site in China is initiated while the phase Ia is ongoing, it is planned the first Chinese patient will be enrolled into the non-CRC dose level that is open at the time of site initiation. Thereafter, at least one Chinese patient will be enrolled in China at each subsequent dose level in phase Ia.

Page 62 of 165

Proprietary confidential information © 2023 Boehringer Ingelheim International GmbH or one or more of its affiliated companies

level and regimen the patient is randomised to. Each treatment Cycle has a duration of 14 days.

Table 4.1.2.2: 1 Dose levels of BI 905711 in phase Ib

Dose (mg/kg)	Dose regimen	Treatment Cycle	Treatment Day
0.6	Biweekly (Q2W)	Cycle 1	Day 1
1.2		Every Cycle thereafter	
2.4			
0.6	Weekly (Q1W)	Cycle 1	Day 1, Day 8
		Every odd-numbered Cycle thereafter	
		Cycle 2	Day 1
		Every even-numbered Cycle thereafter	

4.1.2.3 Dose modification

Patients who experience DLT (Section 5.2.6.1.5) or any grade 3-4 AE possibly related to BI 905711 should interrupt or delay treatment until recovery to CTCAE grade 1 or baseline condition. Restart of BI 905711 treatment can be considered at reduced dose if toxicity is adequately managed and there is approval from the medical representative of Sponsor.

For phase Ia, the subsequent dose level was reduced to the next lower dose level as specified in Table 4.1.2.1: 1 after approval by the Sponsor and provided SMC has agreed the lower dose level is considered safe.

Patients on the first 3 dose levels who continued treatment after completion of Cycle 4, were considered for intra-patient dose escalation to a higher dose level that was determined as being safe and appropriate by the SMC. More than one dose-escalation was considered if deemed appropriate by the Investigator.

For phase Ib, restart of BI 905711 treatment can be considered at a reduced dose by 25% to 50%, if there is approval from the medical representative of the Sponsor.

No more than 2 dose reductions will be allowed. After a dose reduction, no dose re-escalation will be permitted.

At the time the recommended doses for expansion are determined by SMC, patients that are on any other dose levels may be adapted to the recommended dose at investigator's discretion.

Page 63 of 165

Proprietary confidential information © 2023 Boehringer Ingelheim International GmbH or one or more of its affiliated companies

The dose cannot be escalated if the dose has been previously reduced for toxicity reason.

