Archival tumor tissue 12	x ¹²																	
[¹⁸ F]FDG-PET/CT ¹³	x ¹³							x ¹³										
Adverse Events ¹⁴	X	X	X	Х	Х	X	X	X	X	X	X	X	X	X	X	X		
Concomitant Therapy	х	X	X	Х	Х	Х	Х	X	X	Х	X	X	X	X	х	X		
Tumor assessment by CT/MRI RECIST 1.1 ¹⁵	x ¹⁵			•		•			•			x ¹⁵						
Tumor marker ¹⁶	x ¹⁶											x ¹⁶						
Termination of study medication															X			
Patient vital status																		X

^(*) Each treatment Cycle has a duration of 14 days

^(**) Patients who discontinue trial treatment prematurely should undergo the End of Treatment (EOT) visit as soon as possible. If assessments due at EOT are not completed, they may be performed at the 30-Day Safety FUP Visit.

Page 15 of 165

Proprietary confidential information © 2023 Boehringer Ingelheim International GmbH or one or more of its affiliated companies

(***) The 30-Day Safety Follow-up visit is the End of Residual Effect Period visit (EOR) which must happen at the earliest 30 (+ 5) days after the last dose of treatment (see Section 6.2.3.2). †Additional follow-up visits for progression after the 30-Day safety follow-up visit will be performed for patients who discontinue for reasons other than progression or death. Follow-up continues until progression per the imaging schedule (see Section 5.1). The follow-up visits for survival status will be performed every 12 weeks (+/-7 days)(in person or by telephone) until death, lost to follow-up, withdrawal of consent, or end of the whole trial (see Section 6.2.3.3).

For every cycle, the interval between two dose administrations must be always at least 14 days.

¹Written informed consent must be obtained before any protocol specific screening assessments are performed. Re-consenting may become necessary when new relevant information becomes available and should be conducted according to the Sponsor's instructions. Separate consent is to be obtained for optional biomarker sampling.

²Eligibility for further treatment should be confirmed prior to dosing on Day 1 of each cycle from Cycle 2 onwards by confirming the patient has not met any criteria for protocol discontinuation as described in section 3.3.4.1 and absence of any adverse event requiring treatment discontinuation (section 4.1.2.3).

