Tumor assessment by CT/MRI RECIST 1.11	Per institutional practice				
Pregnancy test ²	Per institutional practice ⁶				
12-lead-ECG	Per institutional practice ⁶				
Body weight	X	х			
Administration of BI 905711 ³	X	X	X		
Adverse Events ⁴	X	Х	X	X	X
Concomitant therapy ⁵	x	х	X	X	X
Termination of study medication				X	

^(*) Each treatment Cycle has a duration of 14 days

^(**) Patients who discontinue trial treatment prematurely should undergo the End of Treatment (EOT) visit as soon as possible. If assessments due at EOT are not completed, they may be performed at the 30-Day Safety FUP Visit.

^(***) This combined visit is the End of Residual Effect Period visit (EOR) which must happen at the earliest 30 (+ 5) days after the last dose of treatment (see Section 6.2.3.2).

¹Tumor assessment will be performed according to institutional practices. Images no longer need to be sent to imaging vendor. Only overall response and disease progression will be collected in the electronic CRF.

²Serum and/or urine pregnancy testing to be performed for female patients of childbearing potential as per institutional practice.

³ Dispensing of BI 905711 will be performed via the IRT. Assessment for signs and symptoms of infusion-related reactions and Cytokine Release Syndrome (CRS) is described in Sections 4.1.4.1.1 and 4.1.4.1.2.

⁴ After the individual patient's end of trial: the investigator does not need to actively monitor for new AEs but should only report any occurrence of cancer of new histology, trial drug related SAEs and trial drug related AESIs of which the investigator may become aware of and only via the SAE form, see Section 5.2.6.2.1.

17Apr2023

Clinical Trial Protocol

Page 25 of 165

Proprietary confidential information © 2023 Boehringer Ingelheim International GmbH or one or more of its affiliated companies

Applicable to all patients ongoing patients:

After implementation of CTP v7.0, the patient will have assessments as medically indicated to monitor the safety at the discretion of the investigator. These assessments may include: physical examination, vital sign, safety lab and ECG at a frequency decided by the investigator. The study treatment is administered and the administration information will be documented in the eCRF. Tumour assessment will be performed according to standard of care based on medical opinion of the investigator.

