4.1.4.1 Management of toxicities

4.1.4.1.1 Management of infusion-related reactions

Infusion-related reactions can have different mechanisms. Some are allergic in nature and are usually mediated by immunoglobulin E while others are not classical allergic reactions (so-called anaphylactoid reactions e.g. caused by cytokine release). Although infusion reactions can be allergic or nonallergic, clinical symptoms are difficult to distinguish and require rapid assessment and immediate management to avoid severe adverse events, including fatality.

Page 65 of 165

Proprietary confidential information © 2023 Boehringer Ingelheim International GmbH or one or more of its affiliated companies

If an infusion-related reaction of ≥ CTCAE Grade 3 occurs, study treatment must be permanently discontinued. If symptoms of an infusion-related reaction of CTCAE Grade 2 occur, which do not qualify as DLT according to Section 5.2.6.1.5, the infusion should be temporarily stopped. Upon recovery, the following guidance should be followed:

- If at least 50% of the planned dose of BI 905711 was administered, no further BI 905711 will be administered until the next scheduled dose.
- If less than 50% of the planned dose of BI 905711 was administered due to an infusion-related reaction, a further dose of 50% of the intended total dose may be administered on the following day and after recovery to baseline for at least 24 hours. Administration may occur within up to 3 days after the original planned dose. Refer to Section 10.2 for details regarding PK and biomarker sample collection. Remaining solution from the original dose must be discarded, and a new kit must be dispensed to prepare the dose of 50% of the intended total dose.
- During the first re-exposure, patients must remain under observation for at least 8 hours post start of infusion. If required, patients may be hospitalised for a longer observation period at the investigator's discretion.
- Premedication must be used for all subsequent treatment infusions. The recommended premedication is:
 - o Acetaminophen/Paracetamol 650 mg 1000 mg p.o., or equivalent
 - o Antihistamine p.o. or i.v., equivalent to Diphenhydramine 50 mg i.v.
 - o Glucocorticoid i.v., equivalent to prednisolone 50-100 mg

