4.1.4.1.2 Management of Cytokine Release Syndrome (CRS)

CRS is a disorder characterised by fever, tachypnea, headache, tachycardia, hypotension, rash, and/or hypoxia caused by the release of cytokines. As outlined above in Section 4.1.4.1.1, clinical manifestations of CRS and other forms of infusion-related reactions are difficult to distinguish (especially at first occurrence) and require rapid diagnosis and immediate management to avoid severe adverse events, including fatality.

Patients must remain under observation for potential signs and symptoms of CRS (e.g. hypotension, rash, tachypnea, hypoxia, tachycardia, fever, nausea, fatigue, headache, myalgias and malaise) for at least 8 hours following the end of infusion of BI 905711. If no signs or symptoms of CRS are observed during the first 3 administrations, the duration of observation may be reduced to 4 hours for subsequent administrations. After 6 administrations, in the absence of potential signs and symptoms of CRS, the observation period can be reduced to 2

Page 66 of 165

Proprietary confidential information © 2023 Boehringer Ingelheim International GmbH or one or more of its affiliated companies

hours at investigator's discretion. During all post infusion observation periods, body temperature, pulse rate and blood pressure must be monitored as described in section 4.1.4.

In case of suspected or confirmed CRS, patients will be appropriately treated according to institutional standards and/or medical publications (e.g. R16-2323). Supportive therapy including antipyretics, intravenous fluids, and low dose vasopressors may be used. In patients who do not respond to these treatments, corticosteroids and/or interleukin 6 receptor antagonists (R15-0031, R18-1685, R18-1686) may be required and patients should be monitored closely, preferably in an intensive care unit.

In the event of CTCAE \geq Grade 3 CRS, study treatment must be permanently discontinued. In the event of CTCAE Grade 2 CRS, the guidance for handling a CTCAE Grade 2 infusion-related reaction must be followed (Section 4.1.4.1.1).

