5.2.6.1.5 Dose limiting toxicities

Any of the following AEs will be classified as DLTs, unless unequivocally due to underlying malignancy or an extraneous cause:

Table 5.2.6.1.5: 1 Dose limiting toxicities

Category	Criteria and CTC AE Grade defining a DLT
Hematologic	• Grade 4 neutropenia lasting >7 days.
laboratory	• Grade ≥ 3 neutropenia with documented infection.
	• Grade ≥ 3 febrile neutropenia defined as ANC <1000/mm³ (< 1.0 x 10 ⁹ /L, < 1.0 x 10 ³ /µL) and a single temperature of ≥ 38.3 degrees C (101 degrees F) or a sustained temperature of ≥ 38 degrees C (100.4 degrees F) for more than one hour; or where there are life-threatening consequences or urgent intervention indicated.
	• Grade 3 thrombocytopenia (platelet count \geq 25,000/m³ (\geq 25 x 10 ⁹ /L, \geq 25 x 10 ³ / μ L) and $<$ 50,000/m³($<$ 50 x 10 ⁹ /L, $<$ 50 x 10 ³ / μ L) associated with bleeding excluding grade 1 epistaxis.
	• Grade 4 thrombocytopenia (platelet count <25,000/m³) (< 25 x 10^9 /L, < 25 x 10^3 / μ L).
	• Thrombocytopenia or anemia requiring transfusion per local or international guidelines.
	Neutropenia that requires administration of hematopoietic growth factor agents per local or international guidelines.

Page 79 of 165

Proprietary confidential information © 2023 Boehringer Ingelheim International GmbH or one or more of its affiliated companies

Table 5.2.6.1.5: 1 Dose limiting toxicities (cont.)

Category	Criteria and CTC AE Grade defining a DLT
Non-hematologic laboratory	 Any Grade 3 or Grade 4 non-hematologic laboratory value if: Medical intervention is required to treat the patient, or The abnormality is a serious adverse event, or The abnormality persists >1 week, and considered significant enough to be qualified as DLT in the investigator's opinion, and confirmed by the SMC. An elevated AST or ALT value ≥ 3 x the upper limit of normal (ULN) and an elevated total bilirubin value ≥ 2 x ULN measured in the same blood draw sample and, at the same time, an alkaline phosphatase value < 2 x ULN, as determined by way of protocol-specified lab testing or unscheduled lab testing. An elevated AST or ALT value ≥ 5 x ULN and an elevated total bilirubin value ≥ 2 x ULN measured in the same blood draw sample, with the exclusion of causes due to underlying diseases (for patients with elevated liver enzymes at baseline).

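### Section 4.1.2.3 lets restart be considered after a combined transaminase-bilirubin DLT; a one-clause exception would be a cheap precaution

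*Protocol*

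**What the plan says.** **Restart.** Protocol 4.1.2.3 covers every DLT and every possibly related Grade 3-4 adverse event. Treatment is interrupted or delayed until recovery to Grade 1 or baseline. After that, "Restart of BI 905711 treatment can be considered at reduced dose if toxicity is adequately managed", if the sponsor's medical representative approves. In Phase Ib the cut is 25% to 50%. At most two reductions are allowed, with no re-escalation.

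**Liver DLTs.** Protocol 5.2.6.1.5 counts the listed events as DLTs "unless unequivocally due to underlying malignancy or an extraneous cause". Two criteria combine transaminases with bilirubin:
- AST or ALT at least 3 x ULN with total bilirubin at least 2 x ULN, "measured in the same blood draw sample and, at the same time, an alkaline phosphatase value" below 2 x ULN.
- AST or ALT at least 5 x ULN with total bilirubin at least 2 x ULN, for patients with raised enzymes at baseline, once underlying disease has been excluded as the cause.

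DLTs are recorded for the whole trial, not only in the first two cycles.

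**Mandatory permanent stops.** Section 4.1.4.1.1, for infusion-related reactions at or above the named grade: "CTCAE Grade 3 occurs, study treatment must be permanently discontinued". Section 4.1.4.1.2 has the matching rule for CRS: "Grade 3 CRS, study treatment must be permanently discontinued".

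**Other liver text.** Section 5.2.6.1.4 makes potential severe drug-induced liver injury (DILI) an adverse event of special interest and sends the patient to a DILI checklist held in the data-capture system. Section 3.3.4.1 requires discontinuation when "The patient can no longer receive trial treatment for medical reasons", with adverse events among the examples.

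**The concern.** Section 4.1.2.3 treats a combined transaminase-bilirubin DLT like any other DLT: hold, recover, reduce, and perhaps restart. Yet the DLT definition has already removed cases with a clear alternative cause. Those left are patients with raised transaminases and bilirubin together, in whom the drug has not been ruled out.

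The protocol gives its own reasons for care with the liver. Section 1.4 describes liver as the normal tissue most sensitive to TRAILR2-mediated apoptosis. It reports that a related TRAILR2 agonist was dropped for (reversible) liver toxicity at its first dose level. It also cites one preclinical report that anti-drug antibodies might contribute to liver injury by clustering the receptor. Two other anticipated risks, infusion reactions and CRS, have a firm stop at Grade 3; combined liver injury has none in the readable text. At stake is the re-exposure of an occasional patient on the joint judgement of the investigator and the sponsor, with no written limit.

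**Working it through.** The plan states no figure on this point, so the check is mainly a comparison of sections.

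**1. Does the restart permission reach the liver DLTs?** Yes. Section 4.1.2.3 refers to DLTs as defined in 5.2.6.1.5 without exception, and the two combined criteria are in that table.

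**2. Does any readable section take them out again?**

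| Section | Subject | Permanent stop? |
|---|---|---|
| 4.1.4.1.1 | Infusion-related reactions | Yes, Grade 3 or higher |
| 4.1.4.1.2 | CRS | Yes, Grade 3 or higher |
| 4.1.4.1.3 | Diarrhea, nausea, vomiting | No: delay, consider reduced dose |
| 4.1.4.1.4 | Tumor lysis syndrome | No: manage by guideline |
| 4.1.4.1.5 | Neurological, Grade 2 or higher | Interrupt or stop, unless another cause is documented |
| 4.1.4.1.6 | Proteinuria, Grade 3 or higher | No: interrupt, consider reduced dose |
| 5.2.6.1.4 | Potential severe DILI | Not in the text: report, follow the checklist |
| 3.3.4.1 | General discontinuation | For medical reasons; no liver threshold |

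Section 4.1.4.1 has no liver subsection. The readable text therefore leaves the permission in place. Figure 5.2.6.1.4:1 and the checklist cannot be read here.

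**3. How much re-exposure does the rule allow in Phase Ib?** Assume each cut of 25% to 50% applies to the current dose.
- After one cut: 1 - 0.50 = 50% to 1 - 0.25 = 75% of the original dose.
- After two cuts: 0.50 x 0.50 = 25% to 0.75 x 0.75 = 56.25%.
- Starting from 2.4 mg/kg: 1.2 to 1.8 mg/kg, then 0.6 to 1.35 mg/kg.
- Starting from 0.6 mg/kg: 0.30 to 0.45 mg/kg, then 0.15 to 0.34 mg/kg.

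**4. How often might this arise?** Section 1.2 reports no DLT of any kind in 48 Phase Ia patients. If all 48 count as evaluable, the exact two-sided 95% upper limit is 1 - 0.025^(1/48) = 0.074, or 7.4%. That limit covers all DLT types; combined liver DLTs are a subset. Of the 4 drug-related Grade 3 events in Phase Ia, 3 were AST or ALT rises, all described as transient. Section 1.4 records that the SMC saw no evidence of drug-induced liver injury in data up to 3.6 mg/kg.

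**The case against.** The case against is substantial.

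- **Restart is controlled.** It is a permission, not an instruction. It requires recovery, adequate management, a reduced dose and sponsor approval. DLTs are reported within 24 hours, and safety laboratory tests are at least weekly while a dose is delayed for an adverse event (5.2.3). A reader might infer that patients are re-dosed automatically, or on the investigator's word alone; the text does not support that.
- **The pattern is deliberate.** Hold, recover, reduce is also the rule for severe diarrhea, nausea and proteinuria. The permanent stops are the exceptions, for acute reactions that can be fatal. So the contrast shows a design choice, not a contradiction.
- **Part of the evidence is unseen.** A reader might infer that the trial has no liver stop rule at all. That goes too far: the checklist or the DILI figure could contain one. The readable text describes both only as follow-up and reporting.
- **The risk evidence is mixed.** Hepatocytes lack CDH17, and the drug had no significant effect on the Hep G2 liver cells tested. The protocol says high starting exposure may have contributed to the related agonist's toxicity.
- **Few patients remain.** Development has ended, and the v7.0 charts cover Cycle 6 onward.

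A further reading is tempting. Because v7.0 leaves "safety lab and ECG at a frequency decided by the investigator", one might conclude that liver monitoring has lapsed after restart and that a fixed test schedule is needed. The documents do not support this. Section 1.4 still calls for close liver follow-up throughout treatment, and v7.0 deliberately leaves timing to medical judgement. Once patients with combined injury can no longer restart, such a schedule would fall on patients with other liver events, for whom no case has been made.

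These points limit the weight of the concern, but none of them takes the combined-injury group out of the restart permission.

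**Conclusion.** The point stands as a precautionary, low-cost improvement. As written, 4.1.2.3 permits restart to be considered after a combined transaminase-bilirubin DLT with no unequivocal other cause, and no readable section says otherwise.

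The practical size is small. It concerns only patients still on treatment, whose number is not given, and an event type not seen among 48 Phase Ia patients. The conclusion assumes that the DILI checklist and Figure 5.2.6.1.4:1 hold no dosing rule; if one does, what remains is a missing cross-reference. It also rests on a judgement that little is lost by closing the option, since the sponsor itself gives limited efficacy as a reason for ending development (1.3). It is not evidence that the drug has harmed the liver, and it does not affect any endpoint or analysis.

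**What to change.** Add one clause to 4.1.2.3, for example: *Restart is not permitted, and treatment is permanently discontinued, after (a) a Grade 3 or higher infusion-related reaction or CRS (4.1.4.1.1, 4.1.4.1.2), or (b) a DLT meeting a combined transaminase-bilirubin criterion of 5.2.6.1.5.* If the DILI checklist already contains a stop rule, cite it in place of (b).

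Part (a) repeats existing rules in the section that governs restart; only part (b) is new. The cost is the loss of case-by-case restart in a rare group. That group includes the occasional patient whose rise was probably, but not certainly, due to hepatic progression, and these are patients who have already failed available conventional therapies. No extra blood draws or visits are needed.
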